Subjects will be recruited from three different sites and among the licensed health care provider's test site's pool of patients who are currently being treated for, or who are seeking treatment for Lateral Epicondylitis, or from patients who respond to the following recruitment materials, if needed.

Flyer

WANTED

ADULTS WITH LATERAL EPICONDYLITIS, ONGOING
FOR ONE MONTH, FOR A CLINICAL STUDY
OF THE EFFECTS OF LOW-LEVEL LASER LIGHT ON REDUCING LATERAL
EPICONDYLITIS.

**THIS STUDY INVOLVES SIX LASER LIGHT PROCEDURES, TWO TIMES A WEEKS FOR
THREE WEEKS WITH THE MULTI RADIANCE MEDICAL® MR5® LASER AT THE TEST
SITE.**

THERE IS THREE VISITS PRIOR TO LASER LIGHT PROCEDURES WITH ONE MORE
VISIT TO THE TEST SITE
ONE MONTH AFTER THE LAST LASER LIGHT PROCEDURE.

YOU WILL RECEIVE \$450 IF YOU FINISH THE STUDY.

FOR MORE INFORMATION PLEASE CONTACT:

<PI name>
<test site name & location>
<phone # and/or e-mail>

Newspaper Ad

**Lateral Epicondylitis
Research Study**

This study is to see if the Multi Radiance Medical® MR5® LASER, a non-invasive, investigational device that uses low-level laser light, can help to relieve symptoms of Lateral Epicondylitis pain longer than one month in duration.

The study involves ten visits to a test site and recording some information at home.

You will receive \$450 if you finish the study. Please contact
<PI name> at
<test site name & location> at
<phone and/or e-mail> for details.

Compensation

A subject will be paid a stipend of \$450.00 USD for their participation in the study upon completion. Subjects will not be charged for the cost of the study procedures administered with the Multi Radiance Medical® MR5® Prototype Device for the cost of any other directly related evaluations or measurements that occur as part of his or her participation in the study.

Sample size

There will be 60 subjects evaluated for eligibility in this clinical study:

- 30 subjects in the active procedure group
- 30 subjects in the control procedure group (Placebo)

Rationale for sample size

Based on the following parameters established for the purposes of assessing efficacy of the Multi Radiance Medical MR5 Prototype Device in this clinical study using the Fischer's Exact test to assess the primary endpoint.

- Individual subject success criteria is defined as a 30% or greater reduction in self-reported Degree of Pain rating on the 0-100 VAS from baseline to study endpoint evaluation.

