- Overall study success criteria of at least a 30% difference between the test device group and the placebo group, comparing the proportion of individual successes in each group.
- It is anticipated that about 50% of subjects in the test device group and about 20% of subjects in the placebo group will meet the individual success criteria, and
- Intended application of a two-tailed test with an alpha value of 0.05 and Power of 0.8

- the sample size of 25 available subjects per group (test group and the control group, separately) has been determined using the following reference calculator: *Hypothesis Testing: Categorical Data - Estimation of Sample Size and Power for Comparing Two Binomial Proportions* in Bernard Rosner's *Fundamentals of Biostatistics*.

For the purposes of sample size calculation, a subject loss-to-follow-up of 20% is anticipated.

Therefore, a minimum starting sample size of 30 evaluable subjects in each group is needed to ensure that a sufficient number remains at the end of the trial (25 subjects per group) for any significant differences found between groups to be considered statistically valid and representative of the general population being sampled. This results in a total of 60 subjects being enrolled in this study across both study procedure groups.

RANDOMIZATION

Subject allocation to procedure group will be via variable block randomization with varying block sizes of two and four used at random to minimize the likelihood of predicting the next procedure group assignment. In addition, randomization will be stratified by Fitzpatrick Skin Type grouping

Randomization will be attained using computer generation sequence methodology, ensuring that the randomization methodology and the generated allocation sequence is concealed from the investigator and subjects.

Concealment will be insured as follows:

- Each computer-generated randomization sequence is unique and will therefore not be able to be replicated.
- Randomization will occur to either 'Test Group A' or 'B' rather than to a tests or placebo group, and only the study Sponsor will know which assignment corresponds to the active devices and which corresponds to the fake device. The Sponsor will not reveal this information to any source (investigators, subjects, or study Monitor) until the final study data analysis is complete.

TRIPLE BLIND DESIGN

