This clinical study will be a triple-blind design, such that neither the subject, nor the assessor, nor the therapists will be aware of whether a subject is receiving the study procedure with the active (test procedure group assignment) or the 'fake' (placebo procedure group assignment) Multi Radiance Medical MR5 Prototype Device until after the study is completed.

Maintenance of study triple-blind throughout the entire course of the study will be achieved through the following means:

- Each subject will be randomly assigned to 'Test Group A' or 'B' by the independent study Monitor. Only the study Sponsor will know which label 'Test Group A' or 'B' corresponds to the actual (test) MR5 device and which label corresponds to the 'fake' device until the final study data analysis is complete. The Sponsor will ensure that this information is stored and maintained confidentially at the Sponsor's work site. This knowledge will not be shared with the investigators, the subjects, or the study Monitor until the final data analysis is complete.
- The fake (placebo) MR5 device is designed to have the same physical appearance as the actual MR5 device, including the appearance of any **visible** light output. Therefore, both the test and sham devices emit light when activated that is indistinguishable to both

the subject and to the investigator. As the laser light does not put out any notable degree of heat or noise, these are not distinguishing factors for subjects between the four groups.

3) There will be two independent investigators interacting with subjects at each test site:

- Administration investigator*: who will be responsible for administrating the study procedures; and
- Assessment investigator*: who will be responsible for recording the study outcome measures

Only the administration investigator will be aware of whether a subject is assigned to 'Test Group A' or 'B', although he or she will not be made aware of whether 'Test Group A' or 'B' corresponds to the true or fake laser. Neither the assessment investigator nor the subject will be aware of the subject's A/B Group assignment. In this way, the assessment investigator will not be able to form an association between A/B Procedure Group and active/sham device over the course of the study if a treatment effect is observed.

4) During the MR5 procedures, both the subject and the administration investigator will wear Laser Safety Industries protective eyewear that filter out the laser light spectrum.

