2) **Parametric ANCOVA model** analysis with the mean change from baseline to study endpoint in Lateral Epicondyle pain ratings on the VAS as the dependent variable, procedure group as the independent variable of interest and baseline average Lateral Epicondyle pain VAS rating as a covariate. A two-tailed significance level of 5% will be considered to be statistically significant.

Covariates: The following potential covariate baseline variables will be adjusted, as applicable, through application of an ANCOVA analysis for the continuous variables and linear regression analysis for categorical variables.

- Baseline Lateral Epicondyle pain VAS rating
- Fitzpatrick Skin Type Classification
- Age
- Gender
- Demographics

SUPPORTIVE OUTCOME MEASURES

The following supportive outcome measures will be evaluated:

- a. Mean and individual subject changes in Degree of Pain VAS ratings across and between all study evaluation time points, within and between procedure groups
- b. Mean and individual subject changes in each of the PRTEE, grip strength and TNFa levels measurements across and between all evaluation points, within and between procedure groups
- c. Differences in satisfaction with Study Outcome Ratings between procedure groups at both evaluated time points, and any change between

SUPPORTIVE MEASURES STATISTICAL EVALUATION METHODS

- a. Supportive measures that are continuous variables will be analyzed through parametric analysis using ANCOVA. A two-way significance level of 5% will be statistically significant.
- b. Supportive measures that are categorical will be evaluated through linear regression analysis.
- c. Satisfaction with Study Outcome Ratings: will be tabulated according to category and reported as percentages. Satisfaction levels will be correlated with subject individual study success and recorded changes in Lateral Epicondyle pain VAS ratings from baseline to endpoint evaluations.

STATISTICAL EVALUATION OF APPLICATION OF PAIN MANAGEMENT REGIMEN

The impact of pain management regimen use on the study outcome measure will be evaluated through application of the following analyses:

- a. **Fisher's exact test** to compare the proportion of subjects requiring use of his or her individualized pain management regimen between the test and the control groups.

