Applying stratification according to the process of proportionate allocation using a sampling fraction in each of the strata that is proportional to that of the total sample population, the following formula is applied:

$$X = x1*X + x2*X + x3*X + x4*X + x5*X; \text{ where}$$

- X = Total Sample Population = 50 subjects
- x1 = Subpopulation: White = 0.62; $0.62*50 = 31$ subjects
- x2 = Subpopulation: Hispanic/Latino = 0.17; $0.17*50 = 8.5$ subjects
- x3 = Subpopulation: African American = 0.13; $0.13*50 = 6.5$ subjects
- x4 = Subpopulation: Asian = 0.05; $0.05*50 = 2.5$ subjects
- x5 = Subpopulation: Other = 0.03; $0.03*50 = 1.5$ subjects

Furthermore, in the following reference ...

Sauer's Manual of Skin Disease; Brian J Hall, John C. Hall; 2012

Chapter 35: Skin Disease in Ethnic Skin; [name] & [name] ... Fitzpatrick Skin Type is associated with race, as follows:

- "White": (Not Hispanic/Latino): Fitzpatrick Skin Types I, II & III
- "Ethnic" (Hispanic/Latino; African American, Asian): Fitzpatrick Skin Types IV, V & VI

In consideration of the distribution of race in the U.S population as determined above, this results in the need to recruit:

Ø 31 subjects with Fitzpatrick Skin Type I, II or III

Ø 19 subjects with Fitzpatrick Skin Type IV, V or VI (17 Hispanic/Latino+13 African American+5 Asian+3 'Other')

For ease and uniformity of randomization, given that there will be three test sites, and two procedure administration groups the sampling plan is rounded to even numbers within individual groups, as follows:

Test Site #1		
	Skin Type I, II & III	Skin Type IV, V & VI
Test Group	7	5
Placebo Group	8	4

Test Site #2		
	Skin Type I, II & III	Skin Type IV, V & VI
Test Group	4	3
Placebo Group	4	3

Test Site #3		
	Skin Type I, II & III	Skin Type IV, V & VI
Test Group	4	2
Placebo Group	4	2

While every effort will be made to recruit subjects evenly across the range of Fitzpatrick Skin Types within each of the two categories, it is anticipated that the majority of recruited Skin Types will fall within the range of II to V, inclusive, proportionate within the respective categories, as Fitzpatrick Skin Types I and VI are the least predominant Skin Types amongst the U.S. population.

Once a Fitzpatrick Skin Type category has been filled at a test site, no additional subjects will be enrolled in that category at that site.

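### The VAS ANCOVA omits site although allocation is planned by arm within three sites; adding site is a cheap, modest gain in precision if sites differ

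*Combined protocol and SAP*

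**What the plan says.** All references are to the combined protocol and SAP.

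- **Model.** PRIMARY EFFICACY OUTCOME STATISTICAL EVALUATION METHODS, item 2, takes VAS change from baseline to endpoint as the dependent variable, with "procedure group as the independent variable of interest and baseline average Lateral Epicondyle pain VAS rating as a covariate".
- **Further covariates.** The list that follows opens with "The following potential covariate baseline variables will be adjusted, as applicable". It names baseline VAS, Fitzpatrick skin type, age, gender and demographics. Site is not there.
- **Sites.** Under Recruitment: "Subjects will be recruited from three different sites". Under TRIPLE BLIND DESIGN, item 3: "There will be two independent investigators interacting with subjects at each test site".
- **Allocation.** RANDOMIZATION says that "randomization will be stratified by Fitzpatrick Skin Type grouping" and names no other stratifier. Sample Stratification, however, gives targets for each site, arm and skin-type category: "given that there will be three test sites, and two procedure administration groups the sampling plan is rounded to even numbers".
- **Poolability.** POOLABILITY EVALUATION specifies a Breslow-Day test for the responder endpoint and a treatment-by-subgroup interaction for mean change. The subgroup is not defined, and site is not named.
- **Supportive measures.** Continuous ones are to be analysed by ANCOVA. No model terms are given.

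**The concern.** The sampling tables treat site as part of the planned allocation, but the analysis does not. The sites draw on their own patient pools and have their own treating and assessing staff, so mean change could differ between them. If it does, an ANCOVA without site counts that difference as unexplained error, and the confidence interval for the treatment difference is wider than it need be. The poolability tests do not deal with this. They ask whether the treatment effect varies, and they do not remove average differences between sites from the residual.

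What is at stake is precision in a trial planned on 25 completers per arm. Site should be recoverable for every subject, because the subject ID carries the investigator's initials (PRIVACY AND CONFIDENTIALITY).

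**Working it through.** **The plan's own figure.** The plan gives no SD, precision or power for the ANCOVA. Its only design figure, 25 per group, concerns responder rates of 50% and 20%, with "Intended application of a two-tailed test with an alpha value of 0.05 and Power of 0.8". The pooled two-sided formula gives [1.960·√(2·0.35·0.65) + 0.842·√(0.25 + 0.16)]² / 0.30² = 38.5, so 39 and not 25. That is a separate matter and neither supports nor weakens this point. Only the 25 per group is used below.

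**Inputs from the sampling tables (test/placebo, both skin-type categories added).**
- Site 1: (7+5)/(8+4) = 12/12.
- Site 2: (4+3)/(4+3) = 7/7.
- Site 3: (4+2)/(4+2) = 6/6.
- Total: 25/25, in sites of 24, 14 and 12.

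**Assumed inputs.** Residual SD, treatment effect and ICC (the share of residual variance that lies between sites) are not in the documents. ICC is varied from 0 to 0.20.

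**Step 1: interval width with arms balanced within site.** Half-width = t × SD × √m × √(2/25), where m is the residual variance as a share of the total.
- Without site: 47 degrees of freedom (50 − 3), t = 2.0117, and m = (1 − ICC) + ICC × (50 − Σn²/50)/47. Here Σn² = 24² + 14² + 12² = 916, so 50 − 916/50 = 31.68.
- With site: 45 degrees of freedom (50 − 5), t = 2.0141, and m = 1 − ICC.

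Example at ICC 0.10 and an assumed SD of 20 mm:
- Without site, m = 0.90 + 0.10 × 31.68/47 = 0.9674, and the half-width is 2.0117 × 20 × √0.9674 × 0.2828 = 11.19 mm.
- With site, it is 2.0141 × 20 × √0.90 × 0.2828 = 10.81 mm.

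| ICC | Half-width without site (mm) | With site (mm) | Ratio |
|---|---|---|---|
| 0 | 11.38 | 11.39 | 0.999 |
| 0.05 | 11.29 | 11.10 | 1.016 |
| 0.10 | 11.19 | 10.81 | 1.036 |
| 0.20 | 11.00 | 10.19 | 1.080 |

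The ratio does not depend on the SD, and it passes 1 at an ICC of about 0.004. Simulation on the planned site-by-skin-type cells (20,000 trials per ICC) gave ratios of 1.015, 1.033 and 1.075 at ICC 0.05, 0.10 and 0.20. Coverage of the interval without site was 96.3% at ICC 0.20, so the error is on the conservative side. The interval without site was the wider one in 55% of simulated trials at ICC 0.05 and in 80% at 0.20.

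**Step 2: power.** 8,000 simulated trials per scenario, assumed SD 22 mm and effect 15 mm, baseline VAS in both models. Each power figure has a simulation error of about half a point.

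| ICC | Balanced by site: without → with | Not balanced by site: without → with |
|---|---|---|
| 0 | 0.645 → 0.646 | 0.653 → 0.634 |
| 0.05 | 0.658 → 0.669 | 0.662 → 0.655 |
| 0.10 | 0.671 → 0.693 | 0.670 → 0.676 |
| 0.20 | 0.693 → 0.742 | 0.690 → 0.728 |

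An independent repeat of the unbalanced case gave 0.636 → 0.616, 0.671 → 0.665, 0.661 → 0.662 and 0.687 → 0.726. At ICC 0.10 the unbalanced gain is therefore small: about 1 point, with repeats ranging from almost nothing to about 2.

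**The case against.** The strongest reply is that the benefit is conditional and may be nil.

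- **No evidence on ICC.** Nothing in the documents supports a value as high as 0.20, and at 0.05 the gain is about 1 point at best. This stands.
- **Adding site can cost power.** RANDOMIZATION names only skin type, the site tables cover 50 subjects while 60 are to be enrolled, and subjects are randomised before the stabilization week, after which some may leave. Balance within site is therefore not assured. In that case adding site loses about 2 points at ICC 0 and gains nothing at 0.05. This stands, so the cost is not confined to sites that are identical.
- **Site differences may be small for VAS.** The outcome is change, adjusted for baseline, and the subject marks the line, so assessing staff do not score it. Entry needs a three-day mean of at least 50, and age, gender and skin type may already be adjusted for. This makes a low ICC more plausible for VAS. It applies less to grip strength and TNF-alpha, which depend on procedures carried out at the site.
- **The ANCOVA does not decide success.** The success criteria, hypotheses and sample size all rest on responder proportions compared by Fisher's exact test. This stands.

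A reader might go further and infer that leaving out site biases the treatment estimate. The documents do not support that: the planned arms are equal within every site. If the arms came out unequal by site, the estimate in that one trial could shift by chance, but the plan does not build in such an imbalance. A reader might also infer that the same two-term model is laid down for PRTEE, grip strength and TNF-alpha. The text specifies only ANCOVA for these, without terms.

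**Conclusion.** The omission is real: site is a factor in the planned allocation and is missing from the VAS ANCOVA and its covariate list. Its consequence is conditional. If sites differ in mean change, the interval is on average wider than needed, by about 1.6%, 3.6% and 8.0% at ICC 0.05, 0.10 and 0.20 with arms balanced within site, and it is slightly conservative. In power, adding site is then worth about 0, 1, 2 and 5 points at ICC 0, 0.05, 0.10 and 0.20. With arms not balanced by site, the change is about −2 points at ICC 0, zero or slightly negative at 0.05, about +1 at 0.10 and about +4 at 0.20.

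These sizes rest on an assumed SD, effect and ICC, and on models without the further covariates. Type I error is not threatened, the estimate is not biased if the planned allocation is met, and the study's success decision does not change. This is a cheap improvement in precision and not an error in the plan.

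**What to change.** Before unblinding, amend item 2 and the covariate list so that the VAS ANCOVA contains procedure group, baseline VAS and site (three levels, fixed). Under SUPPORTIVE MEASURES STATISTICAL EVALUATION METHODS, state that the ANCOVAs of PRTEE, grip strength and TNF-alpha contain procedure group, baseline of the same measure and site. Fixing this in advance avoids a choice about site after the data are seen.

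The cost is a change of wording and two degrees of freedom (47 to 45, before any further covariates), with no new data collection. The downside is up to about 2 points of power if sites differ little and arms are unbalanced by site. Fisher's exact test stays as written.
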